#### Title: Clostridium difficile virulence mechanism study (CDVM study)

### Principal Investigator: [name] [name]

#### 1. Research background and objectives

Clostridium difficile is an anaerobic, gram-positive, sporulating bacterium that can give rise to a spectrum of gastrointestinal presentations, including diarrhoea, pseudomembraneous colitis and toxic megacolon. C difficile infection (CDI) is the most common cause of hospital-associated gastrointestinal infection. It accounted for approximately half a million infections and 29,000 deaths in the United States in 2011 (Lessa et al., 2012), and it also represented a major healthcare burden in Canada and across Europe (Bauer et al., 2011). Meanwhile, the hyper-virulent ribotype 027 (BI/NAP1) strain has caused major outbreaks and deaths in North America and Europe. In Asia, the hyper-virulent ribotype 027 was only found sporadically; rather, the ribotype 002 was common in Asia. Our recent work showed that the ribotype 002 was the most common ribotype in Hong Kong (22.8%), and was associated with increased mortality compared to other ribotypes (47.6% versus 12.7%) (Wong et al., 2016). Despite its importance in this locality, there is a paucity of data regarding the virulence mechanism of this ribotype.

This project aims (1) to investigate the virulence mechanisms of C. difficile ribotype 002, by analysing its growth, cytotoxicity, and metabolite production in vitro and in vivo. We also aim (2) to compare these virulence mechanisms with other common ribotypes in Asia, and (3) to correlate these with important clinical outcomes. The results of this study will have a major significance to the medical and scientific community. The mechanistic data will point to important molecular pathways that can be targeted for novel therapies; whereas the phenotypic data will inform us of its virulence and therefore will be useful for disease surveillance and public health interventions. The identified toxin(s) and metabolite(s) may be useful as prognostic biomarkers to stratify patients with different outcomes, as patients with a worse outcome may require more aggressive therapy. Given the prevalence and severity of this ribotype, our CDVM Protocol v3

results will be useful for gastroenterologists, microbiologists, infectious diseases physicians and public health specialists in the Asia Pacific region.

### 2. Methodology

## Study subjects and sample collection

Stool samples will be collected from the in-patients in the Prince of Wales Hospital. Patients newly diagnosed with Clostridium difficile infection will be invited to participate in this study. All participants will sign an informed consent form to be recruited into this study. Clinical data regarding patients' age, gender, medical history, drug history and laboratory test results will be recorded. A fresh stool samples will be collected from the subjects using a 30-mL universal sample container with spoon cap. The stool samples will be delivered to laboratory and stoed at -80 degrees Celsius freezers. All research samples will be de-identified after collection and processing. The study will be conducted in compliance with the Declaration of Helsinki guideline.

Patients must meet the following criteria in order to be enrolled in the study:

1. Patients with a confirmed diagnosis of CDI, as documented by diarrheal symptoms and positive stool test result for C. difficile toxin or toxigenic C. difficile, or colonoscopic findings of pseudomembranous colitis (PMC).

2. Patients aged over or equal to 18 years old.

3. Patients able and willing to provide informed consent.

Patients will be excluded if they meet the following criteria:

- Patients with concomitant infection by other microbes such as Salmonella, Campylobacter, Vibrio, Shigella, and Escherichia coli.
- 2. Patients under 18 years old.
- 3. Patients who cannot give consent.

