### Sample size

Assuming a power of 70% to detect a significant difference at 5% false positive rate, 227 samples will be required at an effect size (Cohen's d) of 0.195.

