# 3. Conclusion

This proposed research aims to collect clinical stool samples to validate virulence mechanisms of different ribotypes of C. difficile being investigated in laboratory work. The study does not involve any invasive or harmful procedure. This important study will inform the characteristics of common ribotypes in Hong Kong to benefit the community.

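### Does enrolling only patients who can consent for themselves undermine the planned correlation with clinical outcomes?

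*Protocol*

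**What the plan says.** Under Study subjects and sample collection, the protocol recruits newly diagnosed in-patients of one hospital and states the consent rule three times. Inclusion criterion 3 requires "Patients able and willing to provide informed consent", exclusion criterion 3 removes "Patients who cannot give consent", and the text adds "All participants will sign an informed consent form to be recruited into this study". No representative or deferred consent is described.

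Section 1 gives as the third aim "to correlate these with important clinical outcomes". Among the expected benefits it says "The identified toxin(s) and metabolite(s) may be useful as prognostic biomarkers to stratify patients with different outcomes". It names no specific outcome. The only outcome figures are mortality from earlier work, 47.6% for ribotype 002 and 12.7% for other ribotypes, with ribotype 002 making up 22.8% of cases. The Sample size paragraph states that "227 samples will be required at an effect size (Cohen's d) of 0.195", with 70% power and a 5% false positive rate. The Conclusion adds that "The study does not involve any invasive or harmful procedure".

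**The concern.** Patients are approached during acute illness, and the disease described in section 1 extends to toxic megacolon. It is plausible that someone too ill to consent is also more likely to do badly. A rule that shuts out such patients would then remove the cases that an outcome correlation or a prognostic marker most needs, and no analysis can recover patients who were never enrolled. Mortality rates and risk differences would be understated, the share of the more lethal ribotype would drift down, and fewer bad outcomes would mean less precision. Since the study takes only a stool sample and involves nothing invasive, a wider consent route looks easy to request.

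**Working it through.** **Consistency.** The inclusion criterion, the exclusion criterion and the consent sentence all say the same thing: every participant consents personally. None contradicts another, and none conflicts with an aim, because no aim claims to cover patients without capacity.

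**Inputs from the protocol.** Mortality p = 0.476 (ribotype 002) and 0.127 (others); share of ribotype 002 = 0.228; N = 227; power 70%; 5% error rate, taken as two-sided. The 227 is taken as given. It is not reproduced from d = 0.195 by a two-sample comparison of means, which needs 650 in total (two-sided), but that is a separate matter and nothing below depends on it.

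**Assumed inputs.** The protocol gives no rate of incapacity. Assume cs = 10% of survivors and cd = 10% to 70% of would-be deaths cannot consent, equally in both ribotype groups. Mortality serves only as an example outcome.

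**Observed mortality** = p(1−cd) / [p(1−cd) + (1−p)(1−cs)].

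For ribotype 002 at cd = 0.7: 0.476×0.3 / (0.476×0.3 + 0.524×0.9) = 0.1428 / 0.6144 = 0.232. For the others: 0.127×0.3 / (0.127×0.3 + 0.873×0.9) = 0.0381 / 0.8238 = 0.046.

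| cd | Mortality, 002 / others | Risk difference | Odds ratio | Share of 002 | Deaths in 227 |
|---|---|---|---|---|---|
| 0.1 | 47.6% / 12.7% | 34.9 points | 6.24 | 22.8% | 46.9 |
| 0.3 | 41.4% / 10.2% | 31.2 points | 6.24 | 21.4% | 38.2 |
| 0.5 | 33.5% / 7.5% | 26.1 points | 6.24 | 19.8% | 28.7 |
| 0.7 | 23.2% / 4.6% | 18.6 points | 6.24 | 18.1% | 18.1 |

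The odds ratio does not move because (1−cd)/(1−cs) multiplies the odds of death in both groups and cancels. The risk ratio rises, from 0.476/0.127 = 3.7 to 0.232/0.046 = 5.0. So only some measures of association weaken.

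**Power for ribotype 002 versus others at cd = 0.7.** Group sizes are 227×0.181 ≈ 41 and 186.
- Unpooled standard error: √(0.232×0.768/41 + 0.046×0.954/186) ≈ 0.068. Power = Φ(0.186/0.068 − 1.96) ≈ 78%.
- With the pooled standard error under the null, √(0.080×0.920×(1/41 + 1/186)) ≈ 0.047: power = Φ((0.186 − 1.96×0.047)/0.068) ≈ 92%.

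Both exceed the planned 70%. At cd = 0.1, 0.3 and 0.5 the second formula gives 99.9%, 99.5% and 98%.

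**Smallest detectable biomarker difference between deaths and survivors** = (1.960 + 0.524) × √(1/deaths + 1/(227 − deaths)).
- cd = 0.1: 2.484 × √(1/46.9 + 1/180.1) = 0.41
- cd = 0.3: 0.44
- cd = 0.5: 0.50
- cd = 0.7: 2.484 × √(1/18.1 + 1/208.9) = 0.61

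With no selective loss the value is already 0.41, about 2.1 times the protocol's 0.195. Most of the distance from that target therefore has nothing to do with consent. Selection on outcome alone also leaves this difference unbiased and costs only precision.

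**Ribotype share.** The largest shift is 22.8 − 18.1 = 4.7 points, against a sampling margin of 1.96 × √(0.228×0.772/227) = 5.5 points. The protocol gives no share for any other ribotype, so no change in ranking can be shown.

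**The case for a change.** The best case for the concern is that the mechanism is plausible, the loss cannot be undone, and eligibility is fixed in the protocol and not in an analysis plan. Absolute mortality and the risk difference do shrink under the assumption, and a drop from 46.9 to 18.1 deaths is a real loss of precision.

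Harsher assumptions also go further. If 90% of deaths and no survivors were lost, power would be 61%. If loss depended on ribotype and outcome together, the odds ratio itself would move. With 10% of survivors, 70% of ribotype 002 deaths and 50% of other deaths lost, it is 6.24 × 0.3/0.5 = 3.75. With 75% and 50% of deaths lost and no survivors, it is 3.12 and power is 61%.

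These results stand as arithmetic, but they show only what could happen. Reverse the pattern, with 25% of ribotype 002 deaths and 75% of other deaths lost, and the correlation (phi) rises from 0.36 to about 0.48, so even the direction is open. The consent basis of the earlier work is also unstated. If it carried a similar restriction, its mortality figures already reflect part of the selection.

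A representative route would be an ethical and legal trade-off, not the repair of a mistake. A bare count of patients lost to incapacity could not test whether they differed in outcome.

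**Conclusion.** The concern does not hold as an error in the plan. The consent rule is stated consistently, contradicts no aim and is a legitimate ethical choice. The harm rests wholly on an assumed link between incapacity and outcome that the protocol neither gives nor implies. If incapacity is unrelated to outcome, nothing is distorted.

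Under equal loss across ribotypes, up to 70% of would-be deaths and 10% of survivors, the odds ratio stays at 6.24 and power for the mortality comparison is at least about 78%, above the planned 70%. The biomarker effect is a loss of precision, from a detectable difference of 0.41 to 0.61, on a contrast the protocol does not name. Prognostic use is mentioned as a possible benefit and is not one of the three numbered aims.

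What survives is a matter of interpretation: absolute outcome rates and ribotype shares will describe in-patients able to consent. Preferring a wider consent route is a design preference.

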## Laboratory and statistical methods

The collected stool samples will be stored at -80C refrigerator. Only one tube of stool sample will be collected from each patient.

Stool filtrate will be used to test for the presence of toxins, including toxin A and toxin B. There are some tests that can be used, including enzyme linked immunosorbent assay (ELISA) and cell cytotoxicity neutralization assay (CCNA). Commercial kits will be used for these assays. Stool DNA extraction can be done to obtain information about toxin A and toxin B through polymerase chain reaction (PCR). Strain typing will also be done to identify the ribotypes of the stool samples collected. This is to also determine which ribotype is the most common ribotype among others.

The statistical software SPSS 13.0 (SPSS, Chicago, IL, USA) and the R Project for Statistical Computing will be used for all statistical analyses. For the microbiome data, the assembly and taxonomical assignment will be performed using the mothur software.

### Sample size

Assuming a power of 70% to detect a significant difference at 5% false positive rate, 227 samples will be required at an effect size (Cohen's d) of 0.195.

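### The stated 227 samples, 70% power and Cohen's d of 0.195 do not agree under any standard Cohen's d calculation

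*Protocol*

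**What the plan says.** The whole justification is one sentence under Sample size in the Methodology. It opens "Assuming a power of 70% to detect a significant difference" and gives its remaining figures as "a significant difference at 5% false positive rate, 227 samples will be required at an effect size (Cohen's d) of 0.195". It names no test, sidedness, number of groups or allocation, and does not say whether 227 is a total or a group size.

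Two other places bear on how to read it:

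- Research background and objectives gives as its second aim "to compare these virulence mechanisms with other common ribotypes in Asia". It also reports from the group's earlier work that ribotype 002 made up 22.8% in Hong Kong and was the commonest type there.
- Laboratory and statistical methods says "Only one tube of stool sample will be collected from each patient", so 227 samples means 227 patients, and patients in different ribotype groups are independent.

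**The concern.** Once the test is chosen, any three of sample size, power, significance level and effect size fix the fourth. The protocol prints all four and names the effect measure, so the sentence can be checked, and it fails.

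This is the protocol's only quantitative planning statement. If a difference of 0.195 SD between two ribotype groups is meant and 227 is the total, the study has less than half the stated power, and a null comparison between ribotypes would say little. If the effect measure is mislabelled, the study may be sized roughly as intended. The text does not let a reader distinguish these cases.

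**Working it through.** **Inputs.** Power 70%, level 5%, d = 0.195 and 227 samples are from Sample size. One sample per patient is from Laboratory and statistical methods. Sidedness, allocation and the meaning of 227 are not stated, so each option is tried.

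**1. Sample size required, two independent equal groups.** The normal approximation is n per group = 2(z_α + z_power)² / d², with d² = 0.195² = 0.038025 and z_power = 0.5244.

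- Two-sided: (1.9600 + 0.5244)² = 6.172, and 2 × 6.172 / 0.038025 = 324.6. The noncentral t gives 326 per group, 652 in total.
- One-sided: (1.6449 + 0.5244)² = 4.706, and 2 × 4.706 / 0.038025 = 247.5. The noncentral t gives 249 per group, 498 in total.

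**2. Sample size required, one-sample or paired test.** Here n = (z_α + z_power)² / d². Two-sided, 6.172 / 0.038025 = 162.3 (noncentral t: 165). One-sided, 4.706 / 0.038025 = 123.8 (noncentral t: 126).

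None of these is 227.

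**3. Power at 227 with d = 0.195.** Power is approximately Φ(d√[n₁n₂/(n₁+n₂)] − z_α). For 227 split 1:1, two-sided: 0.195 × √56.75 − 1.960 = −0.491, so 31.2%, or 31.0% by noncentral t. For 227 per group, two-sided: 0.195 × √113.5 − 1.960 = 0.117, so 54.7%, or 54.5% by noncentral t. All noncentral-t results:

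| Reading of 227 | Power, two-sided | Power, one-sided | d detectable at 70% power, two-sided (one-sided) |
|---|---|---|---|
| Total, split 1:1 | 31.0% | 42.8% | 0.33 (0.29) |
| Per group | 54.5% | 66.6% | 0.234 (0.204) |
| Total, 52 versus 175 | 23.3% | 33.9% | 0.39 (0.34) |
| One-sample or paired | 83.3% | 90.0% | – |

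The third row is an assumption: it applies the 22.8% from the background section (0.228 × 227 ≈ 52, leaving 175) to ribotype 002 versus all others. Over an assumed prevalence of 15% to 30% (34 versus 193 to 68 versus 159), power is 18.1% to 26.8% two-sided and 27.4% to 38.1% one-sided.

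**4. Could 0.195 be a different effect measure?** With N = 227, the noncentrality is 227 × 0.038025 = 8.63 for either ANOVA f or chi-square w.

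| Reading of 0.195 | Power at 227 | N for 70% |
|---|---|---|
| ANOVA f, 3 groups | 74.6% | 206 |
| ANOVA f, 4 groups | 68.3% | 236 |
| ANOVA f, 5 groups | 63.2% | 260 |
| Chi-square w, 2 df | 75.2% | 203 |
| Chi-square w, 3 df | 69.1% | 232 |

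These fall either side of 70%, depending on the number of groups. Four groups or 3 df come closest, but none gives exactly 227 at 70%, and none is Cohen's d.

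**The case against.** **A within-sample contrast.** One tube per patient does not exclude a paired comparison, since several toxin assays may be run on the same stool, and the sample-size sentence is not tied to the ribotype aim. That is fair, but such a test needs 165 or 126, so 227 would be too many rather than correct.

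**A setting that gives 227.** Two exist for a one-sample t-test at d = 0.195. One-sided at 90% power gives 226.6; two-sided at 70% power with the level cut to 0.05/3 gives 226.9. The first contradicts the stated power and the second the stated level.

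**Dropout.** No allowance is stated. Among the Cohen's d readings it could reach 227 only from the one-sample figures, at about 27% loss (1 − 165/227) or 44% (1 − 126/227). The two-group requirement already exceeds 227.

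**A simple mislabelling.** This is a live explanation. Three-group ANOVA needs 206, and an assumed 10% addition makes 226.6, though no such allowance is stated and the match may be chance. If this is the origin, the size may be about right, but the printed effect measure is still wrong.

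**Low stakes, and detail that may sit in the SAP.** The study is non-invasive and takes one stool per patient, and an unstated test or sidedness would not by itself be a fault. The fault is that the printed figures disagree, which no SAP can mend.

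**Fitting the effect to the sample size.** Restating d to suit 227 does not show that the larger d is a relevant difference. That stands, and the fix allows for it.

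**Conclusion.** The sample-size statement is wrong as written and must be corrected. With d = 0.195 and 5%, no one- or two-sided, total or per-group, independent or paired reading gives 227 at 70% power. The nearest two-group reading, 227 per group one-sided, has 66.6% power and is 22 per group short of 249. If 227 is the total for a two-group comparison, power is at most 31.0% two-sided or 42.8% one-sided, because equal groups are the most favourable split.

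The failure does not depend on the prevalence assumption; only the 52 versus 175 figures do. Which input is wrong cannot be settled from the protocol.

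**What to change.** Keep 227 and correct the sentence. State the comparison, the test, its sidedness, the effect measure, the number of groups and whether 227 is a total; then give the power or detectable effect that follows.

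- **If the comparison is ribotype 002 versus all others, two-sided t-test, 227 in total**, possible text is: *With 227 patients, of whom about 52 (22.8%) are assumed to be ribotype 002, the study has 70% power at a two-sided 5% level to detect d = 0.39.* The investigators should say why a difference of that size matters. If 0.195 is the difference of interest, the text should instead admit power of about 23.3%. Comparing 002 with one other ribotype could be called exploratory: 52 versus 52 detects d of about 0.49, and that is a best case if 002 is again the commonest type.
- **If 0.195 is ANOVA f**, say so, give the number of groups, and state the power at 227: 74.6%, 68.3% or 63.2% for three, four or five groups. For four groups, f = 0.199 gives 70%.

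The cost is one sentence in the protocol and no extra patients. Under most readings the stated power or detectable effect becomes less favourable.

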# 3. Conclusion

This proposed research aims to collect clinical stool samples to validate virulence mechanisms of different ribotypes of C. difficile being investigated in laboratory work. The study does not involve any invasive or harmful procedure. This important study will inform the characteristics of common ribotypes in Hong Kong to benefit the community.

